8.2 Baseline Definitions

For safety assessments, the baseline value is defined as the last non-missing measurement taken on or prior to the first dose date. The first dose date is defined as the earliest date of non-zero dose administration of either study drug (ie, lenvatinib or everolimus).

Study day is defined as date of assessment – first dosing date + 1 for any assessment done on or after first dosing date; otherwise, study day is defined as date of assessment – first dosing date.

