9.1.1.2 Baseline Period

The baseline assessment can be performed from Day -3 through Day -1 or prior to randomization on Cycle 1/Day1. The screening assessment can serve as the baseline assessment if performed within 72 hours before randomization. Laboratory tests and a pregnancy test (for female subjects of childbearing potential) may be performed up to 72 hours before randomization.

Subjects who complete the Baseline Period and meet the criteria for inclusion and exclusion ([Sections 9.3.1](#) and [9.3.2](#), respectively) will begin the Randomization/Treatment Phase.

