AEs = adverse events, BP = blood pressure, C1D1 = Cycle 1/Day 1, C1D15 = Cycle 1/Day 15, CT = computed tomography, ECG = electrocardiogram, HR = heart rate, ICL = imaging core laboratory, meds = medications, KPS = Karnofsky Performance Status, MRI = magnetic resonance imaging, MUGA = multigated acquisition, NYHA = New York Heart Association, PET = positron emission tomography, PFS2 = progression-free survival after next line of therapy, PK = pharmacokinetic, RECIST = Response Evaluation Criteria in Solid Tumors, RR = respiratory rate, SAEs = serious adverse events, Tx = treatment.

- a. Subjects must be screened within 28 days prior to randomization. The screening assessment can serve as the baseline assessment, if performed within 72 hours before randomization. Baseline assessments may be performed on Day -1 or on C1D1 prior to randomization. Patients randomized after the baseline assessment must have all baseline assessments reviewed prior to C1D1. Informed consent may be obtained up to 4 weeks prior to randomization.
- b. Efforts should be made to conduct study visits on the day scheduled (±3 days). The study visit (and safety assessments) still needs to occur regardless of a study medication hold per the visit schedule.
- c. KPS assessment will be performed at the Screening and Baseline Visits, on C2D1, and on Day 1 of every subsequent cycle. NYHA assessment will only be performed at the Screening visit. See protocol appendices for KPS assessments and NYHA Cardiac Disease Classification.
- d. TNM staging, according to AJCC criteria (Edge, et al., 2010), should be reported based on the initial diagnosis of RCC.

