- e. Assessments will include vital signs (resting BP [including date and time of measurement], HR, RR and body temperature), weight, and height. Height will be measured at the Screening visit only. One BP assessment is defined as the mean value of 3 measurements at least 5 minutes apart. An elevated BP assessment (ie, systolic BP ≥140 mmHg or diastolic BP ≥90 mmHg) should be confirmed by a repeat assessment after a minimum of 1 hour. Subjects with systolic BP ≥160 mmHg or diastolic BP ≥100 mmHg must have their BP monitored every 2 weeks (on Day 1 and Day 15 or more frequently, as clinically indicated) until systolic BP has been ≤150 mmHg and diastolic BP has been ≤95 mmHg for 3 consecutive months. A diary will be provided to the subject to capture the blood pressure evaluations between study visits. See subsection for [management of hypertensive subjects](#).
Note: During Cycle 3 and subsequent cycles, subjects may return to the clinic for the Day 15 visit if BP monitoring testing is required as specified above. The Day-15 visit is mandatory in Cycles 1 and 2.
- f. A comprehensive physical examination (including a neurological examination) will be performed at the Screening or Baseline Visits, on Cycle 1/Day 15, on Day 1 of each subsequent cycle, and at the Off-Treatment assessment. A symptom-directed physical examination will be performed on C1D1

and at any time during the study, as clinically indicated.

- g. Required if screening physical examination was performed >7 days prior to C1D1.
- h. Single 12-lead ECG. Subjects are suggested to be in the recumbent position for a period of 5 minutes prior to obtaining ECG.
- i. An echocardiogram or MUGA scan to assess LVEF will be performed at Screening and as clinically indicated.
- j. A serum or urine pregnancy test will be performed at the Screening Visit, at the Baseline Visit (or within 72 hours prior to the first dose of study drug), at Day 1 of every cycle (starting with Cycle 2), and at the Off-Treatment assessment in women of childbearing potential (ie, premenopausal and perimenopausal women who have been amenorrheic for less than 12 months).

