- k. Clinical chemistry and hematology results must be reviewed prior to administration of study drug on C1D1 and within 2 business days of receipt of results for all subsequent cycles. Electrolytes such as potassium, calcium, and magnesium should be monitored and abnormalities should be corrected in all subjects before starting treatment per the Investigator's discretion. Clinical laboratory assessments may be conducted anytime within 72 hours prior to the scheduled visit, unless otherwise specified. If there is \geq Grade 3 hematologic or clinical chemistry toxicity, repeat the specific laboratory test and AE assessment at least 3-7 days (until improvement to <Grade 3). For subjects with blood glucose >ULN, a fasting (>6 h, water only) blood glucose sample will be obtained.
- l. Urine dipstick testing for subjects with proteinuria $\geq 2+$ should be performed locally every 2 weeks (on Day 1 and Day 15 or more frequently as clinically indicated) until the results have been 1+ or negative for 3 consecutive months. Urine dipstick testing should be performed preferably at the investigational site (but may be performed locally by the primary care physician or a local laboratory if the subject does not have to come for a visit to the site). If a new event of proteinuria $\geq 2+$ occurs, the subject must resume the Day-15 urine dipstick testing for evaluation of proteinuria until results are 1+ or negative for 3 consecutive months. For subjects with a history of dipstick proteinuria $\geq 2+$, see subsection for [management of proteinuria](#).

Note: During Cycle 3 and subsequent cycles, subjects may return to the clinic for the Day-15 visit if urine dipstick testing is required as specified above. The Day-15 visit is mandatory in Cycles 1 and 2.

- m. Blood samples for PK profiling of lenvatinib and everolimus will be drawn at 0.5-4 h and 6-10 h postdose on C1D1; predose and 0.5-4 h and 6-10 h postdose on C1D15, and predose and 2-12 h postdose on C2D1. If possible, a blood sample for the measurement of the concentration of lenvatinib should be drawn at the first report of an SAE or a severe unexpected AE. A blood sample to measure study drug plasma concentrations will no longer be needed after the data cutoff for the primary analysis.

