9.7.1.8.2 ADVERSE EVENTS

Adverse events will be graded using CTCAE v4.03. The AE verbatim descriptions (investigator terms from the CRF) will be classified into standardized medical terminology using the Medical Dictionary for Regulatory Activities (MedDRA). Adverse events will be coded to the MedDRA lower level term (LLT) closest to the verbatim term. The linked MedDRA preferred term (PT) and primary system organ class (SOC) are also captured in the database.

A TEAE is defined as an AE that emerges during treatment, having been absent at pretreatment (Baseline) or

- Reemerges during treatment, having been present at pretreatment (Baseline) but stopped before treatment, or
- Worsens in severity during treatment relative to the pretreatment state, when the AE is continuous.

Only those AEs that are treatment-emergent will be included in summary tables. All AEs, treatment-emergent or otherwise, will be presented in subject data listings.

An overview table, including the incidence of and the number of subjects with TEAEs, SAEs, deaths, and those TEAEs that led to study drug discontinuation, dose modification, or dose interruption will be provided.

The incidence of TEAEs will be summarized by system organ class (SOC), preferred term (PT), CTCAE grade, and relatedness to study drug. All summaries will be performed by treatment group. Although a MedDRA term may be reported more than once for a subject, that subject will be counted only one time in the incidence count for that MedDRA term with the highest CTCAE grade (in the summary by CTCAE grade) or with the closest relationship to study treatment (in the summary by relatedness to study treatment).

The number (percentage) of subjects with TEAEs will also be summarized by relationship to study drug (Yes [related] and No [not related]).

In addition, the overall proportion of subjects with TEAEs of CTCAE Grade 3 or higher and the overall proportion of subjects with intolerable CTCAE Grade 2 TEAEs that result in dose modification will be summarized.

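### SAP 8.2 sets the safety baseline by date with no pre-dose condition, so any Day 1 blood pressure taken after the first dose would count as baseline

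*SAP*

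**What the plan says.** SAP 8.2 gives one rule for all safety assessments: "the baseline value is defined as the last non-missing measurement taken on or prior to the first dose date". Its anchor is also a date: "The first dose date is defined as the earliest date of non-zero dose administration of either study drug". Neither sentence mentions clock time or requires the value to be pre-dose.

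The protocol describes the Baseline visit in two places. Section 9.1.1.2 says "The baseline assessment can be performed from Day -3 through Day -1 or prior to randomization on Cycle 1/Day1". Table 6 footnote a says "Baseline assessments may be performed on Day -1 or on C1D1 prior to randomization". The treatment-emergent definition in Protocol 9.7.1.8.2 covers an event "having been absent at pretreatment (Baseline", which equates baseline with pretreatment. SAP 5.6.3 does the same.

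Table 6 marks vital signs at Screening, at Baseline and separately on Cycle 1 Day 1. Footnote e lists what is measured: "Assessments will include vital signs (resting BP [including date and time of measurement], HR, RR and body temperature", plus weight. It asks for an elevated blood pressure to be repeated after at least 1 hour; Protocol 9.5.1.4.4 gives at least 30 minutes. On the same day, footnote m has pharmacokinetic samples that "will be drawn at 0.5-4 h and 6-10 h postdose on C1D1".

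SAP 5.6.5 uses the baseline for vital-sign changes at each visit and for the shift table from baseline to worst blood-pressure grade.

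**The concern.** A baseline for a safety summary should be free of drug effect. The rule accepts any reading dated on the day of first dose and takes the latest, so a post-dose Day 1 value would displace both the Baseline-visit value and any earlier pre-dose value that day.

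Blood pressure is where this matters most. Protocol 9.4.2.2 recognizes hypertension as a side effect of drugs that inhibit VEGF signaling. The study compares the safety of two starting doses, and the arms already differ on Day 1. If pressure rises soon after dosing, a post-dose baseline shrinks every later change for that subject and can raise the baseline grade in the shift table. The effect need not be equal in the two arms.

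**Working it through.** The plan states no figure on this point. The check has three parts.

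**1. Can the rule select a post-dose value?**

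| Item | Scheduled on Cycle 1 Day 1? | Pre-dose condition? |
|---|---|---|
| Vital signs, including weight | Yes (Table 6) | None stated |
| Chemistry, hematology, urine dipstick | No (Table 6) | Yes (Protocol 9.5.1.4.3) |
| ECG | No; on-treatment ECGs start at Cycle 2 (Protocol 9.5.1.4.6) | Not needed |

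The protocol states a pre-dose condition for laboratory samples but none for Day 1 vital signs. The repeat of an elevated pressure is a second route to a later Day 1 reading. The exposure is therefore real, but among scheduled assessments it is confined to vital signs.

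**2. What happens when it does?** Take one hypothetical subject. All values are assumed. The first dose is on Day 1 at 09:00.

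| Reading | Systolic (mmHg) | SAP Table 8 grade |
|---|---|---|
| Day -1 | 128 | 1 |
| Day 1, 08:30 | 130 | 1 |
| Day 1, 14:00 (5 h post-dose) | 146 | 2 |
| Cycle 1 Day 15 | 162 | 3 |

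- SAP rule: the first three readings qualify by date and the last of them is 146. Change to Day 15 is 162 − 146 = +16; shift Grade 2 to 3.
- Readings before the first dose only: two qualify and the last is 130. Change is 162 − 130 = +32; shift Grade 1 to 3.
- Without the 14:00 reading, both rules give 130 and identical results.

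The gap between the two changes equals the gap between the two baselines: 146 − 130 = 16 mmHg.

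**3. How large on average?** Let p be the share of subjects whose last Day 1 reading is post-dose, and r their mean post-dose minus pre-dose difference. The mean change from baseline is then understated by p × r at each later visit. The documents give neither quantity. Purely as assumptions:

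- p = 0: 0 mmHg, whatever r is
- p = 0.25, r = 2: 0.25 × 2 = 0.5 mmHg
- p = 0.50, r = 6: 0.50 × 6 = 3 mmHg

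Nothing in the documents supports one of these over another. The sign of r is assumed too: a reading repeated because it was high may be lower the second time, and the error would then run the other way.

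**The case against.** The strongest reply is that no current text places a Day 1 blood pressure after the dose. The post-dose pharmacokinetic draws show only that subjects are at the site, and Table 6 does not tie blood pressure to those draws. If the Day 1 reading is pre-dose, the SAP rule is correct and gives a value closer to treatment than the Baseline visit does. That stands, and it makes the consequence conditional.

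A reader might infer that the rule contradicts a pre-randomization baseline in the protocol. It does not. Section 9.1.1.2 and footnote a set a visit window, not an analysis baseline, and both allow Day 1. A reading after randomization but before the first dose is still pretreatment, so a sound rule must admit some values from the first dose date.

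A reader might also extend the point to the markedly-abnormal laboratory summary in SAP 5.6.4.1. Scheduled laboratory samples are pre-dose and are not repeated on Day 1, so the schedule does not support that. An unscheduled post-dose sample is conceivable, but the point does not rest on it.

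Nor would on-treatment hypertension be lost from view. The shift table still shows the worst post-baseline grade, SAP 5.6.5 lists every subject reaching 140 systolic or 90 diastolic during treatment, and SAP 5.6.3.11 summarizes hypertension as an adverse event.

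Finally, SAP 9 places derivation rules in separate documents, which may already handle same-day values. They are not available here, and the stated definition should be right in its own terms.

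**Conclusion.** The wording gap is real and the point is minor. As written, SAP 8.2 lets an on-drug Day 1 blood pressure serve as baseline. The documents permit this; they do not show that it happened.

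The outputs exposed are descriptive: vital-sign changes from baseline and the blood-pressure shift table. The baseline hypertension subgroup in SAP Table 4 would be touched only if it is derived from this reading, which the SAP does not say. ORR at 24 weeks, the primary safety test, alpha and sample size do not use this baseline.

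The size cannot be derived from the documents. It is zero if all Day 1 readings are pre-dose. An understatement requires both that some are post-dose and that pressure is higher by then. A between-arm difference is possible but cannot be quantified.

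**What to change.** Amend SAP 8.2 so that baseline is the most recent available reading obtained before the first dose of either study drug, comparing date and time where both are recorded. For a reading dated on the first dose date that has no time, or where the dose time is missing, accept it only if it was collected at the Baseline visit or is documented as pre-dose. Otherwise use the preceding value.

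The fallback is needed. Footnote e attaches a time to blood pressure but not to the other vital signs, and the documents do not say that the clock time of the first dose is a database field, although post-dose sampling windows on Day 1 imply that it is known at the site.

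The cost is the revised definition and a small amount of derivation work. The downside is that for some subjects an untimed Day 1 value that was truly pre-dose gives way to the slightly earlier Baseline-visit value. Counting the subjects for whom the two rules differ would show whether any table changes. Where all Day 1 readings are timed and pre-dose, none does.

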8.3 Imputation of Missing Data

Unless specified otherwise, no data imputation will be applied for missing safety and efficacy evaluations. For analysis and reporting purpose, partial dates for adverse events, prior and concomitant therapies, disease diagnosis date, and start date of new anticancer therapy will be imputed if needed. Partial dates for laboratory values, vital signs, and ECGs will not be imputed.

The imputation rules will be specified in study analysis dataset specification with more details.

8.4 Variable Derivations

8.4.1 Duration of Events Prior to Randomization

For the following disease characteristics and prior therapies, the duration in months will be calculated as the date of randomization minus the date of event (disease diagnosis, disease progression, prior therapies, etc.) and then divided by 30.4375.

The duration in years will be calculated as: $(\text{date of randomization} - \text{date of event})/365.25$.

- Time since the first RCC diagnosis to date of randomization (months)
- Time since last disease progression to date of randomization (months)
- Time from end of last therapy to date of randomization (months)
- Time from prior surgery to date of randomization (months)
- Time from last radiotherapy to date of randomization (months)

8.5 Pharmacokinetics/Pharmacodynamics Data Handling

Details on calculating PK parameters, the way that the values of below limit of quantification (BLQ) to be treated, and the analyses to be conducted on PK/PD and exposure-response relationships will be specified in a separate plan.

When developing individual concentration-time profiles, BLQ values will be replaced with 0 for the linear plot or missing for the semi-logarithm plot, respectively.

When calculating the mean or median value for the concentration at a given time point, the BLQ values will be assigned to 0. If the proportion of values reported as BLQ is more than 50%, no summary statistics should be presented at that time point, and the value will be treated as missing in mean or median concentration profiles.

9 PROGRAMMING SPECIFICATIONS

The rules for programming derivations and dataset specifications are provided in separate documents.

10 STATISTICAL SOFTWARE

Statistical programming and analyses will be performed using SAS[®] (SAS Institute, Inc., Cary, NC, USA), Version 9.4 or higher, and/or other validated statistical software as required.

11 MOCK TABLES, LISTINGS, AND GRAPHS

The study tables, listings, and graphs (TLGs) shells will be provided in a separate document, which will show the content and format of all the TLGs in details.

13 APPENDICES

13.1 Efficacy and Futility Boundaries at Each Interim Analysis and Final Analysis

There will be 2 interim analyses and one final analysis. The 2 interim analyses will be performed only in the Per-Protocol Analysis Set 1 (based on investigator assessment). The final analysis will be performed in the Per-Protocol Analysis Set 1 as the primary analysis set, and will also be performed in the Per-Protocol Analysis Set 2 and in the Full Analysis Set as secondary analysis sets.

The tables below list the treatment differences in ORR_{24w} between lenvatinib 14 mg + everolimus arm and lenvatinib 18 mg + everolimus arm corresponding to the efficacy and futility boundaries at each interim analysis for different ORR_{24w} in lenvatinib 18 mg + everolimus arm.

First interim analysis, non-inferiority stopping boundary $OR=1.788$ (non-inferiority will be claimed if observed $OR \geq 1.788$ at first interim analysis. Correspondingly, depending on ORR_{24w} , non-inferiority will be claimed if observed treatment difference between lenvatinib 14 mg arm and lenvatinib 18 mg arm is $\geq \delta$).

ORR_{24w} in lenvatinib 18 mg arm	$\delta =$ Treatment difference (lenvatinib 14 mg arm - lenvatinib 18 mg arm)
10%	7%
20%	11%
30%	13%
40%	14%
50%	14%
60%	13%

First interim analysis, futility stopping boundary $OR=0.590$ (futility will be claimed if observed $OR \leq 0.590$ at first interim analysis. Correspondingly, depending on ORR_{24w} , futility will be claimed if the observed treatment difference between lenvatinib 14 mg arm and lenvatinib 18 mg arm is $\leq \delta$).

ORR _{24W} in lenvatinib 18 mg arm	δ = Treatment difference (lenvatinib 14 mg arm - lenvatinib 18 mg arm)
10%	-4%
20%	-7%
30%	-10%
40%	-12%
50%	-13%
60%	-13%

Second interim analysis, non-inferiority stopping boundary OR=1.436 (non-inferiority will be claimed if the observed OR ≥ 1.436 at second interim analysis. Correspondingly, depending on ORR_{24W}, non-inferiority will be claimed if the observed treatment difference between lenvatinib 14 mg arm and lenvatinib 8 mg arm is $\geq \delta$).

ORR _{24W} in lenvatinib 18 mg arm	δ = Treatment difference (lenvatinib 14 mg arm - lenvatinib 18 mg arm)
10%	4%
20%	6%
30%	8%
40%	9%
50%	9%
60%	8%

Second interim analysis, futility stopping boundary OR=0.962 (futility will be claimed if the observed OR ≤ 0.962 at the second interim analysis. Correspondingly, depending on ORR_{24W}, futility will be claimed if the observed treatment difference between lenvatinib 14 mg arm and lenvatinib 18 mg arm is $\leq \delta$).

ORR _{24W} in lenvatinib 18 mg arm	δ = Treatment difference (lenvatinib 14 mg arm - lenvatinib 18 mg arm)
10%	-0.3%
20%	-0.6%
30%	-0.8%
40%	-0.9%
50%	-1.0%
60%	-0.9%

Final analysis, OR=1.128 (non-inferiority will be claimed if observed OR ≥ 1.128 at the final analysis. Correspondingly, depending on ORR_{24W}, non-inferiority will be claimed if the observed treatment difference between lenvatinib 14 mg arm and lenvatinib 18 mg arm is $\geq \delta$).

[figure not shown]

ORR _{24w} in lenvatinib 18 mg arm	δ = Treatment difference (lenvatinib 14 mg arm - lenvatinib 18 mg arm)
10%	1%
20%	2%
30%	3%
40%	3%
50%	3%
60%	3%

The above boundaries are based on the plan that the two interim analyses will take place when the total number of 150 subjects and 200 subjects in the Per-Protocol Analysis set 1 have completed 24 weeks of follow-up or discontinued early.

Safety and efficacy monitoring will be performed by an independent DMC. The function and membership of the DMC are described in the DMC charter. The recommendations concerning continuation or termination of the trial, or regarding modification of the trial or informed consent documents will be reached by the DMC based on the review of study safety and efficacy data. Determination of whether lenvatinib 14 mg can be used as an alternative dosing strategy will be based on clinical judgment by the Sponsor in consultation with the independent DMC (as specified in the DMC charter) by assessing risks and benefits according to the totality of data at either of the interim or final analyses.

The interim analyses together with the safety monitoring DMC analyses will be performed by an independent statistical reporting team, such as a statistical contract research organization.

SIGNATURE PAGE

Author:		
		Date
	Oncology Business Group, Eisai Inc.	
Approval:		
		Date
	Oncology Business Group, Eisai Inc.	
		
		Date
	Oncology Business Group, Eisai Ltd.
